Previous studies including our own have demonstrated the ability of lipidmodifying drugs, specifically HMG-CoA reductase inhibitors, to induce measurable regression of atherosclerosis. We propose to compare two different approaches to achieve atherosclerotic plaque regression and stabilization using the primary endpoints of carotid atherosclerotic plaque volume and composition defined by MRI. We also propose to measure coronary plaque regression defined by 320 detector row CT angiography, in order to evaluate whether carotid and coronary plaque regression occur in parallel. Finally, we propose to compare the benefit of these two lipid lowering strategies on clinical CV events. In order to achieve all of these objectives, state-of-the-art MRI techniques refined from our previous trial in similar population will be employed to quantify atherosclerotic plaque volume and composition in the carotid arteries, and to measure carotid arterial distensibility and pulse wave velocity. The newest generation of 320 detector CT scanners will be used to measure atheroma volume in the coronary arteries and differentiate between calcified and non-calcified lipid-rich and/or fibrous lesions. We hypothesize that guidance of lipid modifying therapy using imaging assessment of atherosclerosis to intensify or reduce lipid lowering therapy in patients with respectively greater or lesser plague volume at the baseline examination will result in greater plague regression and stabilization than standard NCEP guided therapy with the same or superior safety and/or treatment adherence profiles.

In a subset of individuals we plan to look at plaque inflammation using FDG PET. Molecular imaging compliments traditional anatomical imaging

approaches that identify plaque structure and composition.

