It is widely postulated in the literature that ¹⁸F-fluorodeoxyglucose (FDG) imaging can improve risk assessment and prognostication through the identification of high-risk "vulnerable" plaques, plaques that demonstrate heightened inflammation, neovascularization or apoptosis. The primary target is the carotid and coronary arteries, imaging will also include the ascending and descending aorta, and the iliac arteries. Successful FDG PET imaging has been performed in large vascular beds, including the carotid arteries, and recent preliminary reports suggest the potential for noninvasive coronary plaque imaging. The advantage of nuclear imaging is that multiple vascular beds can be imaged with a single radionuclear isotope administration.

In a subset of 60 individuals we plan to study the reproducibility of arterial stenosis and plaque volume as measured by MDCTA.

At present, there is no available data on the reproducibility of 320 detector row MDCT for measuring arterial stenosis and plaque volume. This data will allow investigators to determine whether measured changes in stenoses and plaque morphology exceed that expected from the limits of measurement error in CTA and thus make the results of ongoing trials more reliable.

Consistent with such objectives, our specific aims are:

1st Aim

To examine whether image guided lipid lowering therapy is superior to NCEP guided therapy in promoting carotid atherosclerotic plaque regression and stabilization.

2rd Aim

To investigate whether the observed change in carotid atherosclerosis volume measured by MR, parallels observed change in coronary atherosclerosis volume measured by MDCT angiography.

3rd Aim

To examine whether MRI guided plaque regression and stabilization produces greater reduction in clinical CV events than standard NCEP guided therapy.

4th Aim

To examine the statin dosages required to promote plaque regression and stabilization differ between conventional and image guided strategies.

5th Aim

To investigate whether FDG PET activity predicts carotid morphological plaque regression and stabilization in both the carotid and coronary arteries and compare the efficacy of PET based prediction with MRI.

6th Aim

To correlate FDG uptake in the carotid, coronary, aortic, and iliac arteries with absolute values and changes in hematological biomarkers of vascular inflammation, thrombosis and atheroprotection at and between each time point.

7th Aim

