3.4 Criteria for removal from Treatment/Protocol

3.4.1 Off Treatment Criteria:

Subjects who come off treatment will be returned to usual care for cardiac risk factors as directed by their primary physician. If they consent to continue imaging follow up, they will complete imaging as per protocol and be analyzed according to their original treatment group assignment.

- 1. Occurrence of a clinical cardiovascular event including myocardial infarction, acute coronary syndrome, angina, heart failure, stroke or revascularization.
- 2. Inability to continue on study medications (adverse reaction, not wanting to adhere to the study medications)
- 3. Inability to reach our study LDL target after 6 months of titration (study visit 4)
- 4. Elevations of liver enzymes three times the upper limits of normal or any elevation accompanied by symptoms compatible with hepatitis, i.e.: fatigue, sluggishness, anorexia and weight loss.
- 5. Myopathy defined as muscle pain with serum creatinine kinase concentrations > 1000 U/L.

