traditional risk-factor based care). This hypothesis will be tested in a study in which subjects are entered and then followed until either (a) the terminal event occurs, or (b) they drop out of the study, or (c) the study ends and the patient is censored while still being actively followed. The study design calls for an accrual period of 50 months and a follow-up period of 24 months. Computation of power for this analysis is based on a hazard ratio of 0.50. Specifically, it assumes hazard rates of 1.00 for the standard care group, versus 0.50 for the image guided group. Since the hazard rate is constant across months, this is equivalent to median survival times of 0.69 years for the standard treatment versus 1.39 years for the image guided intervention group.

The power analysis for the secondary outcome (clinical events) was based on the paper by Brown et al.²⁴ This paper reported mortality rates at 30 months in two treatment groups (2/48 = 0.042 and 3/46 = 0.065) and a control (10/52 = 0.192). We used these rates, as well as the combination for the two treatment groups (5/94 = 0.053). The calculation of power was based on the log-rank test⁽²⁵⁾ assuming a 24 month study. Using a twosided test at the 5% level of significance, we obtained the following results.

 			
Treatment	0.042	0.053	0.065
Mortality Rate			
Sample			
Size/group			
50	0.57	0.47	0.38
80	0.82	0.71	0.59
100	0.91	0.82	0.70

Power of the log-rank to detect the indicated difference from control

We assume that the attrition rate will be 0.20 in the 24-month follow-up. Thus, recruiting 200 study participants with 160 anticipated to complete 24 months of follow-up will be sufficient for this study.

Data Analysis:

1. The intent-to-treat and missing data:

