Standard statistical methods⁽²⁴⁾ will be used to describe the demographic characteristics, clinical manifestations and basic summary statistics as rates or means (medians). Confidence intervals will also be computed. If necessary, permutation methods⁽²⁶⁾ will be employed.

For Hypotheses 1, 2, and 4:

Linear mixed (random-effects) models⁽²⁷⁾ will be used to study differential changes over time in plaque size and composition and drug dosage between the two treatments. Each model will include main effects of time from baseline and treatment, with interactions tested separately. To decide on the correlation structure for these models, variation due to random effects, serial correlation and measurement error will be examined using the variogram. These models will also be used to isolate specific comparisons of outcome variables at specific time points between the two arms. The required assumptions of normally distributed errors and random effects can be checked by an analysis of standardized residuals. which are now available for the mixed model. In the event that the assumptions are not satisfied, usually because of skewed error distributions, data transformations from the Box-Cox power family will be considered. The most commonly used member of this family is the logarithmic transformation, which usually corrects a problem with right skewness.

For Hypothesis 3:

For the time-to-event data, both the Kaplan-Meier estimate and the Cox proportional hazards model will be employed. The primary analysis will compare the two treatments using a log-rank test. Secondary analyses will use the Cox model to include adjustment for covariates. A non-parametric proportional hazards model will also be used to explore possible transformations of independent variables in the models⁽²⁸⁾.

For Hypothesis 5, 6, and 7:

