Using appropriate parametric and non-parametric tests at and between both the baseline and 6 month time points, a comparison of the presence or absence of atherosclerotic plaque by PET and CT / MRI will be performed. FDG accumulation (with both TBR and SUV_{max}) will be compared across different plaque morphology and compositions defined by MR / CT (for example, presence of a lipid core or calcification). Correlation between imaging findings and changes will be made with age, gender, traditional risk factors (height, weight, hypertension, etc.), absolute values and changes in statin dose, total cholesterol, LDL, HDL, triglycerides and hematological biomarkers markers of inflammation, thrombosis and atheroprotection.

For Hypothesis 8:

Agreement between the two blinded readers of semiquantitative measures of CT angiographic stenosis will be measured using weighted kappa. Quantitative analyses of coronary arterial wall volume, lumen volume and plaque composition will be assessed using the intraclass correlation coefficient (ICC) and Bland-Altman plots.

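### Aim 2 asks whether carotid and coronary plaque change run in parallel, but the analysis assigned to it compares the two arms and nothing in the plan relates the two vascular beds

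*Combined protocol and SAP*

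**What the plan says.** Section 1.2 gives the second aim as: "To investigate whether the observed change in carotid atherosclerosis volume measured by MR, parallels observed change in coronary atherosclerosis volume measured by MDCT angiography". The same section explains that coronary regression is to be measured "in order to evaluate whether carotid and coronary plaque regression occur in parallel".

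Section 6.0, Data Analysis item 3, groups Hypotheses 1, 2 and 4 and assigns them linear mixed models, which "will be used to study differential changes over time in plaque size and composition and drug dosage between the two treatments". The terms are specified: "Each model will include main effects of time from baseline and treatment, with interactions tested separately". So is the further use: "These models will also be used to isolate specific comparisons of outcome variables at specific time points between the two arms".

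The documents do not list numbered hypotheses. Reading Hypothesis 2 as Aim 2 is an inference, but the other groupings in section 6.0 match the aims: 3 is clinical events, 4 is statin dose, 5 to 7 are PET and 8 is CT reproducibility.

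Section 1.3 schedules carotid MRI at baseline, 12 and 24 months and coronary CT angiography at baseline and 24 months. Its plaque quantification text already computes coronary wall volume.

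**The concern.** The aim concerns the relation between two vascular beds. The assigned models concern the difference between two arms. A report that followed the plan could show that both beds regressed, or that both differed by arm, without estimating whether the two changes go together.

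Nor does the plan say what parallel means. It could mean that the beds respond alike on average (group level), or that patients whose carotid plaque regresses are those whose coronary plaque regresses (patient level). With no definition, estimand or criterion, the conclusion on a numbered specific aim would depend on which informal comparison is chosen once the results are known. Paired scans that could answer the question directly are already scheduled.

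**Working it through.** **1. Does any other part of the plan relate the beds?**

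- *Hypotheses 1, 2 and 4.* The stated terms are time, treatment and interactions. The correlation structure to be examined by variogram concerns random effects, serial correlation and measurement error. No term or joint model for the other bed is named.
- *Hypotheses 5 to 7.* "Correlation between imaging findings and changes will be made with age, gender, traditional risk factors", and then with statin dose, lipids and biomarkers, at and between baseline and 6 months. Coronary CT angiography is not scheduled at 6 months.
- *Hypothesis 8.* Weighted kappa, ICC and Bland-Altman plots are for CT reproducibility.
- *Power and multiple-outcome text.* Aim 2 is not addressed.

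**2. The plan's own figure.** Section 6.0 gives a baseline mean of 300, an SD of change of 125 mm³, decreases of 40% against 20%, and 80 per arm. The standardised effect is 0.20 × 300 / 125 = 0.48. Two-sample t-test power at 5% is 0.855, against 0.85 stated. This reproduces the carotid power. It says nothing about Aim 2 and is used below only as an effect size.

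**3. What arm tests convey about the patient-level question (illustration).** Assumptions: bivariate normal changes, 80 per arm, and the 0.48 SD effect carried over to the coronary bed, for which the documents give no effect, SD or correlation. There were 20,000 simulated trials per setting. Here ρ is the within-arm correlation of carotid and coronary change.

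| ρ | Arm test rejects, carotid / coronary | Both reject | Arm-adjusted correlation test rejects |
|---|---|---|---|
| 0 | 0.854 / 0.852 | 0.729 | 0.051 |
| 0.3 | 0.852 / 0.855 | 0.747 | 0.972 |
| 0.6 | 0.853 / 0.854 | 0.770 | 1.00 |

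The second column cannot depend on ρ, by construction. The third barely does.

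**4. What they convey about the group-level question.** Treating the SDs as known, the SE of the between-bed difference in standardised arm effect is √[2 × (2/80) × (1 − ρ)], which is 0.224, 0.187 and 0.141 for ρ = 0, 0.3 and 0.6. Multiplied by 1.96, the 95% half-widths are 0.44, 0.37 and 0.28 SD, against an assumed effect of 0.48 SD. Two significant arm tests therefore do not show that the effects are alike.

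**5. Could a direct patient-level analysis work?** Section 6.0 plans on "recruiting 200 study participants with 160 anticipated to complete 24 months of follow-up". Paired scans may be fewer. Patients excluded from iodinated contrast may stay in the study (section 2.2), coronary segments with artifact, blur or stent are dropped (section 1.3), and for patients off treatment, "If they consent to continue imaging follow up, they will complete imaging as per protocol" (section 3.4.1). Values of n below 160 are therefore assumed. Power uses Fisher's z, Φ(atanh(r)·√(n − 4) − 1.96), adjusted for arm:

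| n paired | r = 0.30 | r = 0.24 | r = 0.15 |
|---|---|---|---|
| 160 | 0.97 | 0.86 | 0.47 |
| 120 | 0.92 | 0.75 | 0.37 |
| 100 | 0.86 | 0.67 | 0.32 |
| 80 | 0.77 | 0.57 | 0.26 |

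The last two columns are a true r of 0.30 reduced by an assumed reliability of change, equal in both beds: 0.30 × 0.8 = 0.24 and 0.30 × 0.5 = 0.15. At an observed r of 0.30, the 95% CI is 0.15 to 0.44 for n = 160 and 0.08 to 0.49 for n = 80.

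**6. Why report it with and without adjustment for arm.** Equal arm effects of 0.48 SD add 0.48²/4 = 0.0576 to the covariance and to each variance. The expected unadjusted r is (ρ + 0.0576)/1.0576 = 0.054, 0.338 and 0.622 for ρ = 0, 0.3 and 0.6. The unadjusted value keeps parallel movement produced by the strategies, and the adjusted value removes it.

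**7. Why a correlation is not enough.** A correlation is unchanged when a constant is added to one bed. It could be strongly positive while one bed regresses on average and the other progresses.

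**The case against.** The strongest reply is that Aim 2 is a group-level question. Section 1.1 lists coronary stenosis and plaque volume as a secondary endpoint, and section 7.1 describes the study as comparing two strategies on the progression of both carotid and coronary disease. On that reading, mixed models fitted to each bed are a natural first step. This stands in part. A reader might infer that the assigned models are simply the wrong analysis, or that the aim plainly calls for a patient-level correlation. The documents support neither inference: the models are relevant to the group-level reading but incomplete, because no comparison between beds and no criterion is stated.

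A second reply is that the simulated figures prove little about this trial. That also stands. The independence of the arm tests from ρ holds by construction, and the coronary inputs are assumed. The figures show which question the models address and do not measure harm.

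A third reply is that the aim is not primary and no power is claimed for it. That bears on the weight of the point but does not remove the gap.

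**Conclusion.** The point holds. The analysis assigned to Hypothesis 2 does not answer Aim 2 as worded, and no other section does, so the aim is left to informal side-by-side reading. This rests on taking Hypothesis 2 to be Aim 2.

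The size is moderate: a numbered non-primary aim lacks an estimand, a test and an analysis set. A reader might infer that the primary carotid comparison is weakened or that Aim 2 cannot be answered with these data. Neither follows. The primary endpoint and its power are untouched, and scans in both beds are scheduled at baseline and 24 months. How precise a direct answer would be is uncertain. For a true r of 0.30, power runs from 0.97 (160 pairs, no measurement error) to 0.26 (80 pairs, reliability 0.5).

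**What to change.** For Hypothesis 2, state two analyses and a criterion.

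1. *Group level.* Report the mean 24-month change in carotid wall volume and in coronary wall volume, each as percent of baseline or in SD units, with 95% CIs, overall and by arm. Add the between-bed difference in standardised arm effect with its 95% CI.
2. *Patient level.* Estimate the across-patient association of the two 24-month changes with a 95% CI, unadjusted and adjusted for arm. Use either regression and correlation in patients with evaluable paired scans in both beds, or a bivariate mixed model that extends the models already planned and uses partial data.
3. *Criterion.* Conclude that change is parallel only if the mean changes agree in direction and the association is positive.

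Also state which carotid vessel is used (section 1.1 names the internal carotid; section 1.3 uses the common and internal), restrict the coronary measure to segments evaluable at both visits, and give the number of paired patients.

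The cost is a little more analysis and possibly matching coronary segments across visits. No new scans are needed. Measurement error will pull the correlation toward zero, and the report should say so. Section 7.4 records the study as being in data analysis only since January 2017, so the analysis should be labelled post hoc if it was not specified before the data were seen.

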1.3 Design

Study design: This is a randomized, controlled clinical trial in which 200 men and women aged 55 and older will be randomized to one of two treatment arms. The study duration will be 24 months. The control group will receive standard care with NCEP ATP IIIR guided statin therapy as determined by clinical risk factors. The imaging intervention group will have lipid targets assigned according to the severity of atherosclerotic plaque measured as wall volume in the common and internal carotid arteries by MRI. Patients in the lowest tertile of carotid wall volume (using the MESA study as a reference population⁽⁴⁾) will have statin therapy adjusted to a target LDL between 100-130 mg/dL. Patients in the middle tertile will receive statin therapy to an LDL target of 70-100 mg/dL. Patients in the highest tertile will receive statin therapy to achieve LDL-c levels below 70 mg/dL. Participants will be randomized in a equal ratio into imaging guided and control groups, respectively. This recruitment goal is designed to account for an estimated 20% attrition rate and maintain adequate power at the 24 month endpoint.

Measure	Method	Location	Frequency in the study
Plaque thickness	MRI – with and without contrast	2 carotid sites	Baseline, 12 and 24 months
Plaque area	MRI – with and without contrast	2 carotid sites	Baseline, 12 and 24 months
Plaque volume	MRI – with and without contrast	2 carotid sites	Baseline, 12 and 24 months
Fibrous/Lipid intra- plaque ratio	MRI – with and without contrast	2 carotid sites	Baseline, 12 and 24 months

TreTreatment and Assessments

At the initial study visit, all participants will undergo measurements of carotid arterial wall volume using contrast enhanced MR. For participants randomized to the imaging intervention arm, measured wall volume will be compared against the MESA population, and treatment targets will be assigned according to the magnitude of plaque volume. Participants with mild or no atherosclerosis, defined as the lowest tertile of wall volume, will have statin therapy adjusted to a target range of 100-130 mg/dL Participants in the middle tertile will receive statin therapy adjusted to achieve a target LDL 70-100 mg/dL. Participants with the most severe atherosclerosis will receive statin therapy to an LDL target between 40 and 70 mg/dL. Participants in the control arm will have lipid sub-fraction targets determined according to estimated 10 year cardiovascular risk, as per standard NCEP guidelines.

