Allowable statin compounds and maximum dosages are:

compound	maximum allowable dose	comments
atorvastatin	80 mg /day	
fluvastatin	80 mg/ day	
lovastatin		
(immed. release)	80mg/day	

extended release	60 mg/day	
pravastatin	80 mg/ day	either 40 mg immediate
		release twice daily OR 80 mg
		extended release once daily
rosuvastatin	40 mg/ day	
simvastatin	80 mg/day	

Subjects assigned to both arms of the study will undergo carotid MR for plaque evaluation at baseline, 12 and 24 months of followup. 320 detector row MDCT angiography will be performed at baseline and 24 months. Only unscheduled visits for evaluation of drug toxicity or potential clinical events will not coincide with intervention visits.

Carotid MRI

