Co-investigators blinded to the results of treatment group assignment and patient characteristics will be responsible for the measurement of all MR outcome variables, specifically lumen area, wall volume fibrous content and lipid core. Measurements will be performed using commercially available semiautomatic contouring software (QPlaque, Medis Inc) workstation. Vessel contours will be reviewed by an experienced MR physician. Measurements for the primary study endpoints will be obtained from the post-contrast enhanced sequences as these provide the best definition of the vessel wall and lipid core.⁽⁴⁾ T2 images will be used for confirmation of these measurements on the post-contrast series when necessary. As previously reported, the lipid component of plaque is hypointense on T2 images, while fibrous components are isodense (6-8). The primary study outcome variables will be measured from the 2-D carotid images and derived from these measurements of wall thickness in the radial direction. The calculated area in each slice will be summed for the slices acquired of the relevant vessel, allowing volume calculation of wall and plaque components. Identical measurements will be performed on the 3D sequences for purposes of calculating accuracy and agreement with the current standard 2D approach for use in future investigations.

Coronary angiography by 320 detector row MDCT

1) Coronary calcium scan

Will be performed using the following protocol:

-No contrast.

-CT Imaging: tube voltage = 120kV, tube current = 140 mA, gantry rotation speed = 0.35 seconds, slice thickness = 0.5 mm, rows = 256-320, range = 128-160 mm. X-ray tube will be on for a total of 0.35 seconds. Estimated radiation dose = 1.5 mSv.

2) Rest Coronary arterial imaging

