6.0 Statistical Section

Data from the recently concluded NIA Plaque Study, a randomized double-blind trial of the effect of niacin vs. placebo on MRI plaque volumes were collected on 145 subjects at baseline, and at 18-month follow-up. For the primary endpoint in the proposed study, carotid wall volume, the standard deviation of the differences between 18 months and baseline was 125 mm³, combining data from both the left and right arteries. The baseline mean for the entire group was 300.0. Since the proposed study has a longer duration (24 months) than the NIA Plague Study, and since we have the benefit of improvements in MRI technology, we anticipate a larger effect size than was seen in the NIA Plague Study. The sample size calculations were based on finding a 40% decrease in plaque volume in the image-guided arm compared to a 20% decrease in the conventional treatment arm at 24 months using a two-sample t-test. The table below shows the power to detect this difference at the 5% level of significance, assuming 80 subjects in each group. These power calculations were based on comparing the change from baseline at a single time point. However, the primary analysis will employ a mixed model, which will include multiple observations per patient. Therefore, 80 patients in each group will certainly provide adequate power. As discussed below we assume that the attrition rate will be 0.20 at the 24-month follow-up. Thus, recruiting 200 study participants will be sufficient for this study. These calculations were based on the optimal allocation of equal numbers to the two arms. However a 3/1 ratio of image-guided to conventional therapy did not meaningfully reduce the power.

		Decrease in Plaque Volume (Control Art		
Decrease in		15%	20%	25%
plaque volume	35%	0.85	0.62	0.33
(Image guided	40%	0.96	0.85	0.62
arm)	45%	0.99	0.96	0.85

Power of a two-sample t test to detect the indicated difference in change from baseline at 24 months

For the secondary end-point of this study, the task is to test the null hypothesis that the hazard rate, which is assumed to be constant across all study months, is identical in the two groups (image guided vs.

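### The primary mixed model names no contrast as the primary test and does not adjust for baseline wall volume; the 24-month contrast should be named and baseline adjustment added.

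*Combined protocol and SAP*

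**What the plan says.** Section 6.0 bases the sample size on a two-sample t test of a 40% against a 20% decrease at 24 months, with 80 subjects per arm: "These power calculations were based on comparing the change from baseline at a single time point". It then changes the analysis: "However, the primary analysis will employ a mixed model, which will include multiple observations per patient". From this it concludes: "Therefore, 80 patients in each group will certainly provide adequate power".

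Under Data Analysis, for Hypotheses 1, 2 and 4, the linear mixed models are meant to study how change over time differs between treatments. The stated terms are: "Each model will include main effects of time from baseline and treatment, with interactions tested separately". A later sentence adds: "These models will also be used to isolate specific comparisons of outcome variables at specific time points between the two arms". No time point or coefficient is called primary. For Hypothesis 3, by contrast, the same section names the log-rank test as primary and puts covariate adjustment in a secondary Cox model.

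Section 1.3 says that recruitment is set to "maintain adequate power at the 24 month endpoint", but does not tie this to a model term. It also provides the baseline measurement: "Subjects assigned to both arms of the study will undergo carotid MR for plaque evaluation at baseline, 12 and 24 months of followup". No section uses baseline wall volume as a covariate or constrains the arms to a common baseline mean.

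**The concern.** A mixed model with three scans per patient can yield several tests of treatment: the treatment main effect, a joint arm-by-time interaction, a slope difference, or the arm difference at 24 months. They estimate different quantities and have different power. The plan powers the last and lists the first among its terms. It sets interactions apart for separate testing and makes none of them the primary test. The argument that repeated observations guarantee adequate power therefore depends on a choice the plan does not record.

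Two things are at stake.

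- **Pre-specification.** Section 7.4 says the study has been in its analysis phase only since January 2017. Section 7.6 schedules efficacy analyses at the end of years one and two. A primary coefficient still open at that stage could be chosen with between-arm results in view.
- **Precision.** A baseline scan is planned in both arms, and adjusting for it reduces the variance of the 24-month comparison. The plan does not use it in that way.

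**Working it through.** **Inputs from section 6.0.** Baseline mean 300 mm³. SD of change 125 mm³ (18-month change in the earlier plaque trial). Decrease 40% against 20%, so the difference is 0.20 × 300 = 60 mm³. 5% level; 80 completers per arm (200 randomised, 20% attrition). Sidedness is not stated for the primary endpoint; two-sided reproduces the table.

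**Assumptions not in the documents.** Equal variance at each scan and a common correlation ρ between scans, taken from 0.3 to 0.9. Neither ρ nor the baseline SD is given. Holding the SD of change at 125 makes the cross-sectional SD σ = 125/√(2(1−ρ)).

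**Step 1: the plan's figure.** Standardised difference 60/125 = 0.48, 80 per arm, 158 df, noncentral t: power 0.855 against the stated 0.85. All nine cells of the plan's table reproduce to within 0.01. The 24-month arm-by-visit contrast with an unconstrained baseline is the same comparison, so it also has 0.855.

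**Step 2: the same contrast, baseline-adjusted.** Residual SD = σ√(1−ρ²) = 125√((1+ρ)/2). The variance ratio to unadjusted change is (1+ρ)/2, below 1 for any ρ below 1. Power uses 157 df.

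| ρ | σ | Variance ratio | Adjusted SD | Power, 80 per arm | Completers per arm for power 0.855 |
|---|---|---|---|---|---|
| 0.3 | 105.6 | 0.65 | 100.8 | 0.963 | 53 |
| 0.5 | 125.0 | 0.75 | 108.3 | 0.936 | 61 |
| 0.7 | 161.4 | 0.85 | 115.2 | 0.905 | 69 |
| 0.9 | 279.5 | 0.95 | 121.8 | 0.872 | 77 |

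The last row marks the smallest gain shown: ρ = 0.9 implies a cross-sectional SD of about 280 on a mean of 300.

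**Step 3: the treatment main effect, baseline kept as a response.** The SD of a patient's three-scan mean is σ√((1+2ρ)/3): 77.2, 102.1 and 144.3 at ρ = 0.3, 0.5 and 0.7. The effect is averaged over a baseline at which the arms do not differ.

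| Onset | Effects at 0/12/24 months | Mean effect | Power at ρ = 0.3 / 0.5 / 0.7 |
|---|---|---|---|
| Linear | 0/30/60 | 30 | 0.69 / 0.46 / 0.26 |
| Full by 12 months | 0/60/60 | 40 | 0.90 / 0.69 / 0.41 |

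**Step 4: the average of the 12- and 24-month changes.** Unadjusted SD = 125√0.75 = 108.3. Power is 0.94 if the full 60 mm³ is present at 12 months and 0.74 under linear onset (mean effect 45). With baseline adjustment the SD is σ√((1+ρ)/2 − ρ²). Power at ρ = 0.3/0.5/0.7/0.9 is then 1.00/0.99/0.97/0.95 under early onset and 0.95/0.89/0.83/0.77 under linear onset.

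**The case against.** The strongest reply is that the intent is clear. The models are said to address differential change over time, time-point comparisons are provided for, section 1.3 speaks of a 24-month endpoint, and the power table concerns 24-month change. On that reading the analysis is valid and adequately powered, and a baseline covariate is an improvement rather than the correction of an error. This stands, and it limits the point to a missing designation and an unused gain in precision.

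Three stronger readings are tempting but unsupported.

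- **That the trial is underpowered.** A reader might infer this from the main-effect figures. They need the less natural reading of the model, baseline as a response, and an assumed onset. Section 3.2.1 titrates statins over the first 6 months, so early onset is plausible; at ρ = 0.3 the main effect then has power 0.90, above the planned test.
- **That the 24-month contrast is always the most powerful choice.** It is not. Under early onset the adjusted 12/24-month average does better at every ρ shown, and even the unadjusted average does better at ρ = 0.7 and 0.9. Under linear onset the 24-month contrast is ahead of both. The case for it is that it was the one powered.
- **That a constrained baseline rescues participants who cannot have gadolinium.** Section 1.3 states: "Measurements for the primary study endpoints will be obtained from the post-contrast enhanced sequences". Someone with a known allergy would have no such measurement at any visit, so there is nothing to recover.

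**Conclusion.** The point holds as a gap in specification with an available gain in precision. No test is designated primary for the primary endpoint, and baseline wall volume is not used for adjustment. Unadjusted 24-month change remains valid at power 0.855.

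Naming the 24-month contrast leaves power at 0.855. Baseline adjustment adds about 11, 8, 5 or 2 percentage points at ρ = 0.3, 0.5, 0.7 or 0.9. The direction is secure for any ρ below 1 under equal variances. The size is not, because the documents give neither ρ nor the baseline SD. The figures also carry the 18-month SD of change over to 24 months, as the plan does, and count completers only.

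The documents do not show whether anyone responsible for the analysis has seen results by arm. That decides whether a specification made now counts as prospective.

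**What to change.** Replace the model sentence for the primary endpoint with one paragraph that:

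1. States the primary test as the two-sided 5% arm difference in carotid wall volume at 24 months, from a repeated-measures mixed model with arm, categorical visit, arm-by-visit, baseline wall volume and baseline-by-visit. An equivalent option keeps baseline as a response with its mean constrained equal across arms.
2. Makes every other contrast secondary, including the main effect, the joint interaction, slopes, 12 months and the 12/24-month average.
3. Replaces the assurance that power is certain with the power of the named contrast and the correlation assumed for it.
4. Dates the change and states whether those making it had seen interim or final between-arm results. If they had, the specification is labelled post hoc.

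The cost is that paragraph and the dated statement. No patients, visits or scans are added.
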